	invitations	

A complete list of variables to be abstracted, including justification for variables, is in the table below.

Telephone numbers	Required for screening	
Prior history of CRC	Required for eligibility criteria	
Prior history of CRC resection	Required for eligibility criteria	
Past exposure to CRC	Required for eligibility criteria	
screening tests, including		
colonoscopy, sigmoidoscopy,		
fecal occult blood tests, and		
barium enema		
Insurance type	Required for eligibility criteria	
Incarceration status	If currently incarcerated, not	
	eligible for study	
Screening Outcomes		
Incident CRC	Key outcome	JPS administrative and
Stage of incident CRC	Key outcome	electronic medical record
Date of incident CRC		databases, pathology records,
Treatment for incident CRC		cancer registry data
Incident colorectal polyps	Key outcome	
Size of incident polyps		
Histology of incident polyps		
number of incident polyps		
Completion of CRC screening		
tests, including colonoscopy,		
FIT, fecal occult blood testing,		
barium enema, or		
sigmoidoscopy		-
Date of completion of CRC		
screening tests		
Results of CRC screening tests		
Screening Process Variables/Out	comes	
Number and duration of phone		Program tracking database
Failed mailings		
Wrong phone numbers		

Recruitment Methods and Consenting Process: Recruitment Methods:

Our goal is to recruit all patients who are not up to date with CRC screening, and meeting all of the inclusion/exclusion criteria above, for screening interventions. Recruitment will occur with the following steps:

- a) The administrative and electronic medical record databases at JPS will be used to identify patients age 50 to 64, with at least one primary care visit in the one year period prior to the data pull, who are participants in the JPS Connection medical assistance program for the uninsured. We anticipate that up to 40,000 records may be pulled for this step.
- b) Study inclusion/exclusion criteria will be applied to the dataset.
- c) All patients meeting inclusion/exclusion criteria will be recruited to the study. We anticipate that 20,000 patients will meet inclusion/exclusion criteria, but seek permission to recruit up to 22,000 patients in case the total meeting inclusion/exclusion criteria is higher than expected. This will allow us to deliver screening promotion interventions to all eligible patients.

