we will even have 90% power to detect a smaller screening rate increase of \geq 5% (Power was computed with nQuery Advisor Software v.7.0).

Evaluation Aim B) Compare rates of initial and repeat screening completion among 1) Patients offered a modest financial incentive to complete screening, in addition to outreach invitations (n=2,000), vs. 2) Patients offered outreach invitations alone (n=~18,000). The rate of initial screening completion will be defined by:

Initial	# patients completing a FIT
Screening	Year 1
Completion Rate =	# of patients sent FIT invitation Year 1

We will compare the initial screening completion rate for patients offered the financial incentive, in addition to screening outreach, to the initial rate for patients offered screening outreach alone using a Chi-square test of proportions, with a 2-sided p value <0.05

considered statistically significant. The rate of repeat screening for Years 2 and 3 will be defined by:

Year 2	# patients completing FIT	Year 3 Repeat	# patients completing FIT
Repeat	screening Year 2	Completion	screening Year 3
Completion	# patients completing FIT Year 1	Rate =	# patients completing FIT Year 2
Rate =	with normal result		with normal result

We will compare initial FIT completion rates for the financial incentive plus organized outreach vs. organized outreach alone groups using a Chi-square test, with a 2-sided p value <0.05 considered statistically significant. The same approach will be taken for comparing repeat FIT completion rates for Years 2 and 3.

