Sample size for Evaluation Aim B. The sample size for this aim will be 2,000 for the financial incentive group plus outreach group, and at least 18,000 for the outreach group alone. The sample size for the financial incentive group was chosen based on sample size required for sufficient power to detect expected differences between offers of \$5 and \$10 gift card incentives outlined in Aim C below. The sample size for the outreach group alone was based on including all patients included in the screening outreach program who will not receive financial incentives. With 2,000 patients assigned to the financial incentive plus outreach group, and 18,000 patients assigned to the outreach alone group, we estimate over 90% power to detect differences in initial screening participation of 5% or more at a 5% two-sided significance level. Thus, we will have more than enough power to detect clinically meaningful differences of 10% or more in initial FIT completion. Because of the lack of prior data on repeat FIT participation rates, and under the sample size discussion for Evaluation Aim A above, we do not present formal power calculations for comparisons of repeat FIT completion rates, but expect that we will be able to make meaningful comparisons based on the large number of patients included for evaluation.

Evaluation Aim C) Compare rates of initial and repeat screening among patients receiving \$5 vs. \$10 financial incentives in addition to outreach invitations. For this comparison, we will use the same definitions outlined under "Evaluation Aim B" above for the initial screening completion rate, and the Year 2 and 3 repeat completion rates. For these outcomes, we will compare the outcome rate for patients receiving the \$5 vs. \$10 incentive, using a Chi-square test of proportions, with a 2-sided p value <0.05 considered statistically significant.

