Sample size for Evaluation Aim C. The sample size for Evaluation Aim C is based on comparing the initial screening participation rate between the \$5 vs. the \$10 incentive groups. As is outlined in Section A.3, previous data suggest that financial incentives are effective for promoting complex healthy behaviors such as quitting smoking³⁹⁻⁴¹. Further, we believe that incremental (modest) incentives are likely to significantly increase screening completion. First, we assumed that a 10% or more difference in initial screening participation would be clinically meaningful. Second, we assumed that the screening completion rate associated with the \$5 group would be 43%, and that the rate for the \$10 group would be at least 53%. The 43% rate was chosen because our response to FIT invitations with our prior outreach program was 33%, and we would consider a 10% or more increase Version 8, June 29, 2015

in screening completion associated with the \$5 intervention over organized outreach alone to be clinically meaningful. Similarly, the 53% rate was chosen for the \$10 group because we would consider a 10% or more increase in screening completion associated with the \$10, rather than the \$5 group to be clinically meaningful. Under these assumptions, with an alpha=0.05, we estimated 1090 patients (n=545 in the \$5 group and n=545 in the \$10 group) would be required for 90% power to detect a statistically significant difference of 10% or more in initial screening participation. Because we recognize uncertainty in the estimating the expected difference between the two groups, and because we wanted to increase our ability to conduct exploratory comparisons of repeat FIT participation rates associated with the \$5 and \$10 groups, we increased the planned sample receiving financial incentives to 2,000 (n=1,000 in the \$5 group and n=1,000 in the \$10 group). Thus, we will have more than enough power to detect differences of 10% or more in initial screening participation.

Evaluation Aim D) Assess all CPRIT required outcomes, including increase in early stage cancer detection from baseline, as well as systems changes required to boost screening. To assess increase in early stage cancer detection from baseline, we will compute proportion of CRC patients with early stage cancer at baseline and at end of Year 3. JPS Cancer Registry data will be used for this computation. Rate of early stage cancer will be defined as:

Early Stage	# CRC patients with SEER Summary

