Secondary analyses. We plan to conduct several secondary analyses. First, we recognize that results from Evaluation Aim A, in which baseline screening rates will be compared to follow up screening rates at year 3, could be confounded by time trends in CRC screening rates, which generally have been increasing over time. Accordingly, we will compare the observed rate of CRC screening in Year 3 to the expected rate of CRC screening based on time trends in screening at JPS. The expected rate will be estimated using the secular trend for CRC screening using annual screening rates for each of the 7 years 2006-2011 prior to start of our prevention program in 2012. All rates will be standardized by gender and age strata (50-54, 55-59, and 60-64 years) to the population distribution of men/women and these age strata for 2012, and a standardized incidence ratio (SIR) will be computed. An SIR greater than 1, with an associated 95% confidence interval that does not cross 1 will be interpreted as evidence to support impact of our outreach intervention beyond time trends in CRC screening rates. We have previously used this approach to assess impact of a University of Texas health plan policy that waived copays for colonoscopy screening on CRC screening rates which began in 2009, in which we compared colonoscopy uptake 2002-2008 to uptake after policy institution⁴⁶.

Version 8, June 29, 2015

Second, to identify factors independently associated with screening outcomes, we will construct several logistic regression models. For example, to identify predictors of initial screening completion, we will create a model using initial screening completion rate as the primary outcome (dependent) variable, and several potential predictors of completion. Predictors considered for model inclusion will include age, sex, race/ethnicity, frequency of primary care visits, exposure to the screening outreach program, and exposure to financial incentives. A similar model will be created with the outcome of programmatic screening as the dependent variable. For these exploratory analyses, 2-sided p values of 0.05 will be considered statistically significant.

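### Aims B and C use valid but unadjusted chi-square tests with no effect estimate or interval; prespecified adjustment for baseline variables already extracted would be a small, nearly free gain

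*Combined protocol and SAP*

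**What the plan says.** Under Biostatistics, Evaluation Aim B, the analysis is a crude two-group test: "We will compare initial FIT completion rates for the financial incentive plus organized outreach vs. organized outreach alone groups using a Chi-square test". Evaluation Aim C compares $5 with $10 "using a Chi-square test of proportions, with a 2-sided p value <0.05 considered statistically significant". Neither aim names an effect measure or a confidence interval. The only interval in the evaluation plan belongs to the standardised incidence ratio under Secondary analyses.

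The sample size for Aim C assumes that the $5 "group would be 43%, and that the rate for the" $10 "group would be at least 53"%. It continues: "Under these assumptions, with an alpha=0.05, we estimated 1090 patients", 545 per arm, who "would be required for 90% power to detect a statistically significant difference of 10% or more in initial screening participation". The plan then enlarges this to 1,000 per arm, partly because the true difference is uncertain.

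The table of variables to be abstracted (Sources of Research Material) lists sex, race/ethnicity, primary language, date of birth and "Past exposure to CRC" screening tests, the last for eligibility. Visit dates are extracted under Data Sources and Data Tracking. Every enrolled patient is, by the inclusion criteria, not up to date with screening.

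Under Secondary analyses there is an adjusted logistic model of initial completion: "Predictors considered for model inclusion will include age, sex, race/ethnicity, frequency of primary care visits", together with exposure to outreach and to financial incentives. It is labelled exploratory.

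**The concern.** In a randomised comparison, adjusting for baseline variables that predict the outcome narrows the interval without adding patients. Here the variables are in hand and the main analyses do not use them. The incentive arms also filled in Year 1 (Sub-Study Procedures), so Aim C can gain no more patients.

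The Financial incentives section says the purpose of Aim C is to learn the smallest incentive that changes participation. That is a question about the size of a difference, possibly one below 10 points. A p-value alone does not answer it; a risk difference with an interval does. The exploratory model does not fill the gap. Its covariates are only candidates, language and past screening are not among them, and it does not say that $5 and $10 will be separated.

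**Working it through.** **1. Reproduce the plan's figure.** Inputs from Evaluation Aim C: 43% v 53%, two-sided alpha 0.05, power 90%. The pooled-variance formula gives

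n = [1.960·√(2·0.48·0.52) + 1.282·√(0.43·0.57 + 0.53·0.47)]² / 0.10² = 522.5, so 523 per arm.

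With continuity correction, n' = (n/4)·[1 + √(1 + 4/(n·0.10))]² = 542.3, so 543 per arm. The plan states 545, so the figure is reproduced.

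**2. Unadjusted power for Aim C at 1,000 per arm.** Power = Φ{[d·√n − 1.960·√(2·p̄·(1−p̄))] / √(p₁(1−p₁) + p₂(1−p₂))}.

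- 43% v 53%: Φ[(3.162 − 1.385)/0.703] = Φ(2.53) = 99.4%.
- 43% v 48%: Φ[(1.581 − 1.380)/0.703] = Φ(0.286) = 61.2%.
- The difference detectable with 80% power from a 43% base is 6.25 points.

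**3. Unadjusted power for Aim B.** Take 38% in 2,000 incentive patients and 33% in 18,000 standard patients. The pooled rate is 0.335, the null standard error 0.01112 and the alternative standard error 0.01141. Power = Φ[(0.05 − 1.960·0.01112)/0.01141] = Φ(2.47) = 99.3%. This agrees with the plan's claim of over 90%.

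**4. What the documents say about predictive strength.** They give no R², odds ratio or FIT-return rate by any baseline variable. The only computable figure is race/ethnicity against up-to-date status in Table 1. The overall rate is 1 − 10,319/16,905 = 0.3896, with variance 0.3896·0.6104 = 0.2378. Weighting each group's squared deviation from 0.3896 by its share of 16,905:

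- White, 34.0%: 0.000886
- Black, 39.9%: 0.000019
- Hispanic, 42.5%: 0.000354
- Other, 44.0%: 0.000294

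The sum is 0.001554, and R² = 0.001554/0.2378 = 0.0065. This concerns a different outcome (prevalent screening status) in a different population (all clinic patients), so it does not estimate prediction of FIT return.

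**5. Gain from adjustment in Aim C.** R² for FIT return has to be assumed. The approximation is effective n = 1,000/(1 − R²), with the interval half-width multiplied by √(1 − R²). The unadjusted half-width at 43% v 48% is 1.96·√(0.43·0.57/1,000 + 0.48·0.52/1,000) = 4.36 points.

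| Assumed R² | Effective n per arm | Power, 43% v 48% | Detectable at 80% power | 95% half-width |
|---|---|---|---|---|
| 0 | 1,000 | 61.2% | 6.25 points | 4.36 points |
| 0.01 | 1,010 | 61.7% | 6.2 points | 4.34 points |
| 0.05 | 1,053 | 63.5% | 6.1 points | 4.25 points |
| 0.10 | 1,111 | 65.8% | 5.9 points | 4.14 points |

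At 43% v 53%, power moves only from 99.4% to 99.7% over the same range. For scale, a predictor that splits patients in half needs a 20-point gap in FIT return to reach R² = 0.25·0.20²/(0.43·0.57) = 0.041. Reaching 80% power at 43% v 48% takes 1,556 per arm, hence R² = 1 − 1,000/1,556 = 0.36.

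**The case against.** The strongest reply is that nothing is broken. A chi-square test on a randomised two-by-two table is valid, the sample is nearly twice what the design required, and an adjusted model containing incentive exposure is already planned. Preferring an adjusted analysis is then a matter of taste. Most of this stands. What it leaves open is that the planned model is exploratory and cannot be relied on for the $5 v $10 contrast, and that no interval is promised for either aim.

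Three stronger readings are tempting, and the documents support none of them.

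- *The plan discards strong predictors.* No figure for FIT return is given. Past screening is the natural candidate, but eligibility narrows it: no stool test within one year, sigmoidoscopy within five or colonoscopy within ten. Lapsed testers still differ from never-tested patients, but how many there are and how differently they respond is not stated. The spread across race/ethnicity in Table 1 amounts to an R² of 0.0065 and cannot carry the argument.
- *Power for $5 v $10 is thin.* The plan calls 10 points clinically meaningful and has 99.4% power there. Power falls below 80% only for differences under about 6.25 points, and adjustment at any R² in the assumed range would not restore it.
- *The Aim B test is confounded by later invitees.* Standard invitations continued after the incentive arms filled, and the quoted comparator of about 18,000 looks like the whole programme. But the initial completion rate is defined on Year 1 invitations, so the documents do not show that later invitees enter the test. Invitation round within Year 1 is still worth adjusting for, because the documents do not say in which rounds incentives were being assigned.

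**Conclusion.** The point holds as a minor, nearly free improvement. The primary comparisons are valid but leave baseline information unused, and they promise no effect estimate or interval. The gain in precision is modest: for an assumed R² of 0.01 to 0.10, Aim C power at 43% v 48% rises by about 0.5 to 5 percentage points, to between 62% and 66%, and the 95% half-width shrinks by at most about 0.2 points. At the plan's own targets the gain is negligible. The more useful return is a stated risk difference with an interval for the choice between $5 and $10.

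This rests on the assumed R² range, which the documents neither support nor exclude; on the n/(1 − R²) approximation for a marginal risk difference; and, for Aim B, on the plan's figure of 18,000, since the number of standard invitations in Year 1 is not given.

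**What to change.** Before results by arm are examined, prespecify for initial completion in Aims B and C a covariate-standardised risk difference with a robust 95% confidence interval, from a logistic model with marginal standardisation.

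- **Covariates:** age, sex, race/ethnicity, primary language, number of primary care visits before invitation, past exposure to CRC tests, and invitation round.
- **Population:** Year 1 invitees, as the plan's definition of the initial rate already requires. For Aim B, standardise over rounds in which incentives were being assigned, because a round with no incentive patients carries no information on the contrast.
- **Contrasts:** any incentive v none for Aim B, and $10 v $5 for Aim C, each named explicitly. State how missing covariate values are handled.
- **Sensitivity analysis:** keep the planned chi-square tests.

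Limit this to initial completion. The repeat-completion denominators consist of patients who had already completed a test, so they are formed after randomisation and baseline adjustment does not restore the randomised comparison.

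The cost is a paragraph in the analysis plan and standard code. Every variable is already extracted or held in the tracking records, and no patients or data are added. If results by arm have already been seen, report the adjusted estimate as supportive and say so.

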The incentive will consist of either a \$5 or \$10 gift card to a local retailer that will be sent to the patient upon return of an FIT kit. Incentives will be mailed by the JPS outreach team, in exchange for successful FIT completion, after the FIT has been returned. \$5 and \$10 incentives were chosen for several reasons. First, these levels of incentives, if shown effective, could be potentially sustained by the JPS system beyond the timeframe of the grant. Higher incentives, while potentially more powerful in inducing participation, would be unsustainable and therefore do not merit study at this time. Comparing \$5 and \$10 incentives is important because if offering incentives is effective in boosting screening, it is important to know the minimum incentive required for meaningful changes in participation. Incentives are to be offered to all patients who are assigned to the incentive strategy. We considered, but rejected, restricting incentives to only patients who initially do not respond to screening invitations. This was because restricting incentives to non-responders would logistically complicate outreach activities. It is important to note that patients meeting study inclusion criteria must have a minimum of 1 visit to a JPS Primary Care clinic within the last year. Considering these patients have an established baseline relationship with the JPS primary care system, the addition of a modest financial incentive should not create undue influence in patients that otherwise would still have exposure to information on the benefit of screening. Since participation in this standard of care screening poses minimal to no risk, the chances that incentives may motivate research participants to take unnecessary risks are low.

Screening Completion Follow Up. Follow up for determining screening completion for all included patients will be through the end of Year 3 regardless of whether or not patients respond to screening invitations. As is explained below, screening rates will be measured for all patients included for outreach invitations. For patients who die on follow up or who do not have additional health system encounters, follow up will be censored at time of death or last health encounter, respectively.

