 HEDIS criteria were selected because these are standardized criteria that the National Committee on Quality Assurance uses to compare rates of CRC screening across different insurance carriers. The criteria are clear, and widely available, and using these criteria will improve generalizability of our program procedures. In prior published analyses, we previously demonstrated ability to determine screening rates and identify patients not up to data using a similar approach, and validated the approach for this purpose^{19, 42}. Table 3 shows codes that will be used to assess whether patients are screening up-to-date.

Criteria for Exclusion of Subjects:

Patients with a history of CRC or colon resection, no address and/or phone number on file, or who are incarcerated will be excluded. Patients with history of CRC/colon resection will be excluded because they require specialized screening, usually with colonoscopy. Addresses and phone numbers are required to deliver outreach. Incarcerated patients will be excluded because they cannot keep FIT kits in their cells.

Once included, patients will remain in the program unless they no longer meet age criteria. Patients in both the standard (non-incentive) and incentive invitation groups who do not respond to initial invitation will be followed for screening outcomes, but will not receive repeat

Version 8, June 29, 2015

invitations. Through the program period, we expect that some patients will no longer participate in the JPS connection program, or not see a primary care provider within a year. We considered excluding these patients in subsequent years, but decided against this. Many of these patients remain uninsured, and if they were to develop late stage CRC, would present to JPS for treatment. We anticipate that most of these patients would then again access the JPS medical assistance program for the uninsured as well as primary care clinics, because JPS is the main safety-net health system for uninsured patients in Tarrant County and Fort Worth, TX. Continuing screening outreach will potentially allow for boosting detection of such patients when their CRCs are early, rather than late stage.

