Individuals in the age range from 50 to 64 are most likely to benefit from CRC screening²³. Modeling studies suggest that a life expectancy of at least 8 years is required for a given patient to realize the benefits of screening over non-screening¹³. In fact, one group has suggested that Medicare consider supporting screening for those under 65, as this could prevent CRC associated morbidity and mortality when individuals acquire age of Medicare eligibility²⁴.

Biostatistics: EVALUATION STRATEGY

Overview. Our overarching evaluation goal is to rigorously evaluate program outcomes. The evaluation will be strengthened by our prior experience and systematic approach to evaluating program outcomes. Our evaluation strategy has been designed to provide the most interpretable results possible, and position local and state public health officials to assess program impact and areas for improvement. The evaluation will be lead by [name], a biostatistician, [name], an epidemiologist, and [name], a physician and clinical researcher. We have a track record of completing sophisticated program evaluations, and have worked together on prior analyses. We have developed several primary evaluation aims, as well as a number of secondary evaluation aims. It should be noted that all CPRIT required program evaluations are addressed.

Consistent with Goal 3, for our primary evaluation aims, we will:

Evaluation Aim A) Determine screening rate improvement after expanding screening outreach to all unscreened patients. We predict the population screening rate will be $\geq 10\%$ higher after outreach expansion compared to baseline.

Evaluation Aim B) Compare rates of initial and repeat screening completion among 1) Patients offered a modest financial incentive to complete screening, in addition to outreach invitations, vs. 2) Patients offered outreach invitations alone.

Evaluation Aim C) Among patients receiving financial incentives to complete screening, compare rates of initial and repeat screening completion between patients receiving \$5 vs. \$10 incentives.

Evaluation Aim D) Assess all CPRIT required outcomes, including increase in early stage cancer detection from baseline, as well as health system changes required to boost screening.

Approach to Evaluation Aims

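### Aims B and C test repeat FIT completion only among prior-year completers, a subset the incentive is planned to change, so the test does not estimate the incentive's effect on repeat screening

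*Combined protocol and SAP*

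**What the plan says.** Under Evaluation Aim B, the initial completion rate is taken over everyone sent a Year 1 invitation and compared between arms by chi-square at two-sided 0.05. For the repeat rates, "The same approach will be taken for comparing repeat FIT completion rates for Years 2 and 3". Their denominators are different. The Year 2 rate divides by "patients completing FIT Year 1" with a normal result, and the Year 3 rate divides by Year 2 completers with a normal result. Evaluation Aim C takes over the same definitions for the initial rate "and the Year 2 and 3 repeat completion rates", with the same test.

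The Biostatistics overview introduces Aims A to D with "Consistent with Goal 3, for our primary evaluation aims, we will", so repeat completion sits inside the primary aims. The sample-size text for Aim C is less firm: one reason for enlarging the incentive groups was to "increase our ability to conduct exploratory comparisons of repeat FIT participation rates" between the 5- and 10-dollar groups. No such label is attached to the repeat comparison in Aim B.

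The same text gives the planned uptake. "The 43% rate was chosen because our response to FIT invitations with our prior outreach program was 33" percent, and a further 10 points takes the 10-dollar group to at least 53%.

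**The concern.** Completing the Year 1 FIT is a response observed after randomisation, and it is the response the incentive targets. If the incentive works as planned, its Year 1 completers are a mixture: people who would have returned the kit anyway, and people who returned it because of the gift card. The outreach-alone arm has only the first kind. Comparing repeat rates between these subsets mixes any effect on repeating with a change in who is in the denominator. The Year 3 rate conditions in this way a second time.

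The comparison could then show a deficit, no difference or a gain that is not the effect of the incentive. A spurious deficit could be read as incentives undermining annual adherence, and a real gain could be hidden. The Background says that FIT screening is effective only with annual testing, so this is a question readers will look to the trial to answer.

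**Working it through.** **The plan's own figure.** For 43% vs 53%, two-sided alpha 0.05 and 90% power, the normal-approximation formula gives 523 per group, or 543 with continuity correction. The plan states 545, so its figure is reproduced. That calculation, and the stated power for Aim B, concern initial completion among all invited patients and are not touched by this point. The plan gives no power for the repeat comparisons.

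**Inputs from the documents.** Year 1 completion 33% (outreach alone), 43% (5 dollars) and 53% (10 dollars); abnormal FIT 12%, so 88% normal; 18,000 vs 2,000 patients for Aim B and 1,000 vs 1,000 for Aim C. Aim B pools the two incentive groups, so planned uptake is (43+53)/2 = 48%; 43% is also shown.

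**Assumed.** The incentive only adds completers and does not change the Year 2 behaviour of those who would complete anyway. They repeat at rate ra, and induced completers at ri. Under Evaluation Aim A the plan cites 40 to 75% for repeat participation overall, with nothing for induced completers.

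**Formula.** With p0 and p1 the completion rates in the lower- and higher-uptake arms:

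- conditional rate in the higher-uptake arm = (p0 × ra + (p1 − p0) × ri) / p1
- spurious difference = (1 − p0/p1) × (ri − ra)

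The induced share, 1 − p0/p1, is 10/43 = 23% at 43% uptake, 15/48 = 31% at 48%, and 10/53 = 19% for 10 vs 5 dollars. The bias vanishes only if ri = ra or p1 = p0.

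**Aim B, Year 2, ra = 60%.** Denominators: 18,000 × 0.33 × 0.88 = 5,227 for outreach alone; 2,000 × 0.43 × 0.88 = 757 or 2,000 × 0.48 × 0.88 = 845 for incentive.

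| Uptake | ri | Conditional rates | Difference (points) | p |
|---|---|---|---|---|
| 43% | 40% | 60.0 vs 55.3% | −4.7 | 0.015 |
| 43% | 50% | 60.0 vs 57.7% | −2.3 | 0.22 |
| 43% | 60% | 60.0 vs 60.0% | 0 | n/a |
| 43% | 70% | 60.0 vs 62.3% | +2.3 | 0.22 |
| 48% | 40% | 60.0 vs 53.8% | −6.3 | 0.0006 |
| 48% | 50% | 60.0 vs 56.9% | −3.1 | 0.09 |

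The result is significant against the incentive when ri is about 44% or less (43% uptake) or about 48% or less (48% uptake).

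**The same patients, all randomised.** For the first row, the proportion with a normal Year 1 FIT and a Year 2 FIT is 0.33 × 0.88 × 0.60 = 17.4% vs 0.43 × 0.88 × 0.5535 = 20.9%, z = 3.9 in favour of the incentive. The two analyses point in opposite directions.

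**Masking, 43% uptake.** Suppose the incentive does raise repeating among those who would complete anyway. A rise from 60% to 66% shows as no difference if ri = 40%: (0.33 × 0.6606 + 0.10 × 0.40)/0.43 = 0.600. With ri = 50%, a rise to 63% disappears.

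**Aim C, 43% vs 53%.** Denominators are 1,000 × 0.43 × 0.88 = 378 and 1,000 × 0.53 × 0.88 = 466. With ra = 60% and ri = 40%, 60.0% vs 56.2% (−3.8 points, p=0.27). With 75% and 40%, 75.0% vs 68.4% (−6.6 points, p=0.035). Equal rates give zero.

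**Number of Year 1 controls.** The initial rate counts Year 1 invitations, but standard-invitation patients also entered later. Assuming 10,319 − 2,000 = 8,319 Year 1 controls (10,319 being the number needing screening in 2011), the 60%/40% case at 43% uptake gives p=0.023.

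**The case against.** The conditional rate is a legitimate quantity. Initial non-responders are not re-invited, so completion among those offered a second kit answers the programme's question of whether participation stays high when FIT is offered annually. The plan says it will compare rates and does not call the repeat contrast a causal effect. This stands as a reason to keep reporting the rate. It does not support a between-arm test at 0.05 within a primary aim about incentives, which will be read as an effect of the incentive.

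The size is assumed. At 43% or 48% uptake a 10-point gap in repeat rates is not significant, and with only a 5-point gain in uptake the 60%/40% case gives −2.6 points, p=0.19. The 43% and 53% are sample-size assumptions, not forecasts. All true: the point is that the test lacks a randomised interpretation, not that it must mislead.

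The all-randomised outcome does not isolate repeating either. At 43% uptake with equal 60% repeat rates it shows 17.4% vs 22.7% (+5.3 points), all from Year 1. This also stands, and is why it must be reported beside the initial rate.

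Finally, the logistic models under Secondary analyses include incentive exposure and baseline covariates. The only outcomes they name are initial completion and a programmatic screening outcome that is not defined. They are exploratory, and baseline covariates may not remove the selection. They do not repair the repeat test.

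**Conclusion.** The concern holds and should be fixed. The planned repeat comparisons in Aims B and C condition on a post-randomisation response that the plan itself expects to differ by arm, and nothing elsewhere corrects for it. On the planned rates, and if the incentive only adds completers, 31% of the pooled incentive denominator (23% at 43% uptake) and 19% of the 10-dollar denominator relative to 5 dollars would be there only because of the incentive or its larger amount.

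In the Aim B illustrations the spurious Year 2 difference runs from −6.3 to +2.3 points, with zero when repeat rates are equal. These sizes rest on assumed repeat rates, and no direction is claimed. The weight is lower for Aim C, where the sample-size text calls the repeat comparison exploratory.

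**What to change.** For the between-arm repeat comparison in Aims B and C:

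- Take as denominator all randomised patients sent a Year 1 invitation, restricted by baseline age if wanted.
- Take as outcome completion of the FIT due in Year 1 and in Year 2, and separately through Year 3, with one pre-stated analysis rule for abnormal FITs applied equally to all arms.
- Report it beside the initial completion rate, and say that it combines the effects on initial and repeat completion.
- Keep the conditional rates as descriptive adherence among re-invited patients, without a test of incentive effect.

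Two small clarifications belong in the same edit. State that the numerators of the conditional rates are limited to members of their denominators, because the follow-up section also re-invites Year 1 normals in Year 3, whether or not they completed Year 2. State whether the 5- vs 10-dollar repeat comparison is primary or exploratory.

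The cost is a few sentences. The data are already planned: under Screening Completion Follow Up, follow-up "for all included patients will be through the end of Year 3 regardless of whether or not patients respond to screening invitations", and the exclusion section confirms that patients in both groups "who do not respond to initial invitation will be followed for screening outcomes". The downside is that the reported rates will look lower, and the new outcome cannot by itself separate sustained repeating from the Year 1 gain.
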